Aim 1c. Cost of intervention: The HCCC and the Clinician will log time spent providing services, excluding research activities. Costs will be assigned to staff time based on prevailing national wage rates. Patient time costs will also be estimated based on time spent with staff members and will be valued based on the minimum wage because most patients are likely to be unemployed. We will describe patient-reported health care visits, employment, and incarceration that will be used as inputs to future cost or cost-effectiveness studies.

Aim 1d. Safety: Because concern about side effects has been cited as a reason not to treat PWID for hepatitis C, and because experience with these drugs in PWID has not been reported, we will report prospectively collected data on safety outcomes on all participants who receive antiviral therapy. All treatment-emergent side effects (e.g., fatigue, headache, nausea, insomnia, irritability, anorexia, diarrhea, constipation, etc.) will be tabulated, as will adverse events, including abnormalities in serum bilirubin, liver enzymes, infections, hospitalizations, and deaths), and any adverse effects requiring treatment discontinuation, according to OHRP152 and NIH153 guidelines. We will describe the frequency of side effects, adverse events, and treatment-limiting outcomes, among all study participants who received at least one dose of antiviral medication. If numbers permit, we will compare the rates in the two arms to see whether AC influences perceived side effects.

Aim 1e. Reinfection: We will report reinfection rates in all patients in both arms who achieve SVR using time-to-event methods. If 150 participants initiate antiviral therapy (50% overall) and 120 (80%) of those achieve SVR, with 2%/month attrition (21.5%/yr), we will have 198.3 person-years of follow-up when data collection is concluded, enough for a reasonably robust estimate.

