5. At the medical evaluation, about 20mL (4teaspoons) of blood will also be drawn by one of the other research staff members, and sent to New York Presbyterian Hospital. The blood will be tested to assess participants' health and liver. A small percentage of the blood drawn will be stored at the Weill Cornell Medical College Clinical and Translational Science Center for future testing of characteristics of your hepatitis C virus.
6. We will schedule participants to come back in 2 weeks to find out the results of your blood tests. Participants and their hepatitis C doctor will work together to make an informed decision about whether participants will take medication used to treat hepatitis C. The doctor will explain the risks and benefits of taking any medicines before you take them. The medications the doctor will prescribe are the current best standard of HCV treatment available. If the doctor recommends that the participant take these medications, participants will be free to decide whether or not to take them.
7. If participants take the medication for hepatitis C, they will get appointments to come back to pick up their medication. Hepatitis C medications prescriptions will be sent to specialty pharmacies, and when obtained, delivery of medication will be to the harm reduction facility or patients residence if novel coronavirus is an issue.
8. If participants begin treatment for hepatitis C, standard blood tests for monitoring the treatment will be performed by a members of the research staff (or commercial lab testing centres if novel coronavirus is an issue), at weeks 2, 4 and 12 of treatment, and 4 and 12 weeks after the end of treatment. In addition, an extra two teaspoons of blood may be drawn at each of these visits for research purposes and sent for storage at Cornell's Clinical and Translational Science Center. These samples may be tested to look for signs of multiple concurrent hepatitis C infections, and help to decipher treatment failure from re-infection in participants who do not achieve cure of their hepatitis C.
9. If participants start the medications used to treat hepatitis C and want to stop them before their treatment is finished, they are free to do so and will not be penalized in any way, although this could limit the success of hepatitis C treatment. Participants will be encouraged to continue with the study questionnaires every three months.

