10. Within 6 months of enrolling in the study, participants will have a one-on-one meeting with a hepatitis C study coordinator to review harm reduction practices. This discussion will include discussions on prevention of hepatitis C transmission and re-infection, ways to engage in safe injection practices and avoid cross-contamination of injection equipment while injecting with others.
11. Data from participants' clinical medical records will be entered into our research database during the course of your treatment by a members of the research staff. These data include, but are not limited to, hepatitis C genotype, hepatitis C viral load, fibrosure results(looking for signs of cirrhosis), HIV antibody, sustained virologic response (defined as no detectable hepatitis C virus 12 weeks after completing therapy), and any side effects or adverse effects you experience during therapy

If participants agree to take part in this study and are assigned to Group B, participants will have the following tests and procedures:

Group B –Usual Care Group (Hepatitis Care at usual locations in the community): If assigned to this group, participants will participate in research visits but not receive hepatitis care or treatment at the Lower East Side Harm Reduction Center as part of the study. Participants can obtain care and treatment for hepatitis C at the usual locations in the community.

Research Visits (every 3 mos): Information that will be collected for the study will consist of (1) detailed questionnaires, and (2) one or more extra blood tests. The details of the study are as follows:

1. Questionnaires will be administered every three months for up to 12 months, independent of whether participants receive treatment for your hepatitis C, with questions about their demographics (e.g., age, gender, race), their alcohol and drug use history and practices, sexual practices and experience with health care.
2. One teaspoon of your blood will be drawn and sent to New York Presbyterian Hospital –Weill Cornell Translation Science Center where it will be processed and stored for potential future testing of characteristics of your Hepatitis C virus.
3. Human Immunodeficiency Virus (HIV) testing as described above will be offered at a research visit every 6 months to those participants who previously tested negative for HIV.

Hepatitis Care and Treatment:

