4. Participants will be referred to a hepatitis C case manager (funded through the New York City Department of Health Check Hep C Program), on site at their harm reduction facility (Lower East Side Harm Reduction Center), who will assist participants with referral for hepatitis C care within the community.
5. If participants start treatment for hepatitis C during their time in the study, we will ask participants to give us permission to talk with their hepatitis C doctor so we can have access to their medical records and monitor how they are responding to treatment.
6. If participants achieve a sustained virologic response after completing hepatitis C treatment, which means that the treatment was successful, participants will be given an appointment to come back every three months to complete a study interview and be tested for hepatitis C, for up to 144 weeks after treatment completion, to find out whether they are still negative, or to see whether they get re-infected.

QUALITATIVE INTERVIEWS During the study, we may ask participants to take part in an interview about their experiences related to hepatitis C treatment. This will last about 60-90-minutes. If participants choose to participate, the interview will be digitally audio-recorded. If participants are selected for this interview we will ask participants about: health care and hepatitis C-related healthcare experiences, alcohol and drug use, injection risk behaviors and sexual practices. We will ask participants how these changed, if they did, during their taking part in the study.

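### Laboratory abnormalities are reported among all dosed participants, but on-treatment bloods are scheduled only in Accessible Care, so the rate is understated to the extent that Usual Care results are missing

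*Combined protocol and SAP*

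**What the plan says.** Section 4.2.1, Aim 1d, promises that "we will report prospectively collected data on safety outcomes on all participants who receive antiviral therapy". The events to be tabulated include "adverse events, including abnormalities in serum bilirubin, liver enzymes, infections, hospitalizations, and deaths", and their frequency is to be described "among all study participants who received at least one dose of antiviral medication". No post-dose laboratory result is required for a person to count in that denominator. If numbers permit, rates are to be compared between arms, with perceived side effects given as the purpose.

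Section 7.1 describes blood sampling differently by arm:

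- **Accessible Care (Group A, item 8).** For those who begin treatment, "standard blood tests for monitoring the treatment will be performed by a members of the research staff", with a commercial laboratory as the pandemic alternative, "at weeks 2, 4 and 12 of treatment, and 4 and 12 weeks after the end of treatment".
- **Usual Care (Group B).** Participants will "not receive hepatitis care or treatment at the Lower East Side Harm Reduction Center as part of the study". Their research blood (item 2) is "processed and stored for potential future testing of characteristics of your Hepatitis C virus". No on-treatment monitoring schedule is given. If they start treatment (item 5), "we will ask participants to give us permission to talk with their hepatitis C doctor so we can have access to their medical records".

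Section 4.1 adds two provisions for both arms. Laboratory results and adverse events are to be abstracted from the Weill Cornell record or requested from other facilities. Participants on therapy are interviewed monthly about adherence and side effects.

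**The concern.** A frequency among everyone dosed is sound when everyone dosed is looked at in the same way. That is planned for side effects, through the monthly interviews. It is not planned for chemistry: one arm has a protocol schedule, and the other depends on outside ordering and record release. A starter with no post-dose chemistry cannot show an abnormality, yet still counts in the denominator.

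Aim 1d is justified by the lack of reported experience with these drugs in people who inject drugs, so its laboratory rate may be reused as safety evidence. A rate diluted by untested people would be falsely reassuring. A by-arm version could make Accessible Care look worse simply because more blood was drawn. Section 9.1 asks whether the intervention is sufficiently safe, but Section 9.2 contains no safety analysis, so Aim 1d is the only place where the rule is set.

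**Working it through.** **The plan's own figures.** Section 9.4 gives 80% power with 150 per arm for initiation of 66% against 50%. At a two-sided alpha of 0.05 (sidedness is not stated) this reproduces as 80.5%. That figure says nothing about laboratory safety; it is used here only as a source for the number of starters.

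**Inputs from the documents.**
- Section 9.4 example: 0.66 × 150 = 99 Accessible Care starters and 0.50 × 150 = 75 Usual Care starters, 174 in all.
- Section 4.2.1, Aim 1e: 150 starters in total (50% of 300), split by arm not given.

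The two totals disagree, so three splits (Accessible Care/Usual Care) are carried:
- 99/51: 99 as above, with 150 − 99 = 51.
- 99/75: the power example.
- 75/75: an equal split of 150.

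**Assumptions.** All Accessible Care starters have usable post-dose chemistry. True risk is equal in the arms. A share u of Usual Care starters has no retrievable post-dose result. The documents do not give u.

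**Formula.** Let A and U be the starters in Accessible Care and Usual Care.

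Reported rate ÷ true rate = [A + (1 − u) × U] ÷ (A + U)

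Relative shortfall = u × U ÷ (A + U)

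**Results (relative shortfall of the pooled laboratory rate).**

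| u | 99/51 | 99/75 | 75/75 |
|---|---|---|---|
| 0 | 0% | 0% | 0% |
| 0.25 | 12.75/150 = 8.5% | 18.75/174 = 10.8% | 18.75/150 = 12.5% |
| 0.50 | 25.5/150 = 17.0% | 37.5/174 = 21.6% | 37.5/150 = 25.0% |
| 1 | 51/150 = 34.0% | 75/174 = 43.1% | 75/150 = 50.0% |

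For scale, take a true rate of 10% (assumed). With u = 0.50 the pooled report would be 8.3%, 7.8% or 7.5% for the three splits. By arm, Accessible Care would show 10% and Usual Care 10% × 0.50 = 5%, with no real difference between them.

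**With a tested-only denominator.** Under the same assumptions untested starters leave both parts of the fraction, so the ratio is 1 and a true 10% is reported as 10%.

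**The case against.** The strongest reply is that Usual Care laboratory data have a planned source. Section 4.1 provides for abstraction from the Weill Cornell record or from other facilities. It also gives both arms access to the same study physicians and says treatment follows standard clinical protocols. The Accessible Care bloods are themselves described as standard monitoring, and nothing says that community clinics omit them. Item 8 does not name bilirubin or liver enzymes either, so full testing in Accessible Care is also an assumption.

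This stands against a stronger reading. A reader might infer that Usual Care starters are untested by design, that the plan counts untested people as normal, or that toxicity as a whole is understated. The documents support none of these:
- Record abstraction may supply some or all of the Usual Care results.
- No rule assigns a normal result to the untested. The rule in Section 4.2.1 that unmeasured means not reached is written for the care-continuum outcomes.
- Side effects are asked about monthly in both arms, and Section 8.3 has adverse events asked about at each study visit.
- Section 8.1.1 counts an abnormal result as an adverse event only if it meets a listed condition, such as symptoms, further tests or clinical significance. Minor elevations found by extra testing would not automatically count.

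The between-arm comparison is also conditional and aimed at perceived side effects. However, the sentence on comparing rates follows a list that includes adverse events, and laboratory events are not excluded.

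What the reply does not remove is the denominator. Abstraction retrieves tests that were done and released; it does not create a schedule. Nothing says how a starter without a post-dose result is handled.

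**Conclusion.** The point holds conditionally and for laboratory abnormalities only. To the extent that Usual Care starters lack a retrievable post-dose result, the stated denominator dilutes the pooled rate, and a by-arm rate would partly measure testing intensity.

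The size cannot be fixed from the documents. With half of Usual Care starters lacking a result, the pooled rate would be about 17% (99/51), 22% (99/75) or 25% (75/75) too low in relative terms. This assumes complete testing in Accessible Care and equal risk. There is no understatement if Usual Care results are complete and equally frequent. The 34% to 50% row requires that no Usual Care result at all be retrieved; given the planned abstraction it is an outer bound, not an expectation.

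The output is descriptive. The primary endpoint and the power statement do not depend on it, and the review triggers in Section 8.1 (treatment-related serious events, overdose-related hospitalizations and deaths, and overall deaths) are not laboratory frequencies. The change is still worth making, because readers of a laboratory safety rate need to know how many people were tested.

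**What to change.** Amend Aim 1d and carry the same text into Section 9.2:

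- For bilirubin and liver-enzyme abnormalities, use as denominator the starters with at least one post-dose result.
- Beside the all-dosed count, show by arm the number tested and the tests per person.
- State that laboratory abnormalities are described and not compared between arms.
- Keep any between-arm comparison to side effects from the monthly interviews, which both arms receive.

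The cost is wording and table shells, with no added blood draws. The denominator is smaller and the intervals wider. A tested-only denominator could also overstate the rate if Usual Care tests were prompted by symptoms, and requiring at least one result does not equalise testing frequency. Showing both denominators and the tests per person makes these limits visible. If Usual Care results prove complete, the reported rate hardly changes.

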8.1 Specification of Safety Parameters

We anticipate that providing HCV care and treatment on site at a community syringe exchange center will allow access to treatment for greater numbers of people who inject drugs (PWID). Treatment on this study will include FDA-approved standard of care regimens with excellent safety profile; however limited data exists on the use of these agents in PWID. While experts have little concern for drug-drug interactions between most DAAs and illicit drugs, we have chosen to monitor HCV Treatment-related SAEs, Hospitalizations and Deaths related to Overdose, and Overall Deaths as safety endpoints that would trigger review of the study. Other on treatment side effects will also be captured and described, but will not impact conduct of the study and thus will not be reported to DSMB. Currently, HCV cure rates exceed 90% with currently available all oral DAA regimens in clinical trials and recent clinical cohorts regardless of HCV genotype; however little is known about treatment efficacy and safety in active drug users as these patients are typically excluded from clinical trials. One clinical trial of a modern era DAA regimen was conducted in 301 persons receiving opioid agonist therapy (OAT) (Merck C-EDGE Co-STAR) and provides some safety and efficacy data relevant to our study. It did not exclude patients who were actively using drugs of potential abuse, and more than 50% of patients had at least one urine drug screen positive for potential drugs of abuse. The study randomized patients to the fixed dose combination of elbasvir/grazoprevir or placebo, so that safety could be carefully ascertained in this patient population perceived as being high risk for unrelated adverse events. Those that received placebo were subsequently treated open label. The primary efficacy outcome showed an SVR 12 of 91.5% in the immediate treatment group and 89.5% in the delayed treatment group. Positive urine drug screens did not affect adherence or efficacy. 18 patients had recurrent viremia and 5 were due to probable reinfection. The safety profile was similar between treatment and placebo with rare SAEs (3.5% in treated, 4% in placebo); however, only 1 SAE in each group was considered treatment-related. The high efficacy and relative safety of this study of patients on OAT, many of who also used drugs of potential abuse, is reassuring that HCV treatment may be safely delivered to our study population.

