8.3 Time Period and Frequency for Event Assessment and Follow-Up

The occurrence of an AE or SAE may come to the attention of study personnel during study visits and interviews of a study participant presenting for medical care, or upon review by a study monitor. All AEs including local and systemic reactions not meeting the criteria for SAEs will be captured on the appropriate RF. Information to be collected includes event description, time of onset, clinician's assessment of severity, relationship to study product (assessed only by those with the training and authority to make a diagnosis), and time of resolution/stabilization of the event. All AEs occurring while on study must be documented appropriately regardless of relationship. All AEs will be followed to adequate resolution.

Any medical condition that is present at the time that the participant is screened will be considered as baseline and not reported as an AE. However, if the study participant's condition deteriorates at any time during the study, it will be recorded as an AE. UPs will be recorded in the data collection system throughout the study.

Changes in the severity of an AE will be documented to allow an assessment of the duration of the event at each level of severity to be performed. AEs characterized as intermittent require documentation of onset and duration of each episode.

The PI will record all reportable events with start dates occurring any time after informed consent is obtained until 7 (for non-serious AEs) or 30 days (for SAEs) after the last day of study participation. At each study visit, the investigator will inquire about the occurrence of AE/SAEs since the last visit. Events will be followed for outcome information until resolution or stabilization.

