9.2 Statistical Hypotheses

Specific Aim 1: Hepatitis C Outcomes.

Hepatitis C treatment engagement. We will assess the proportion of patients in each arm who (a) referred to a hepatitis C treatment provider, (b) attend an initial visit with a hepatitis treatment provider, and (c) complete a medical evaluation for antiviral treatment, including a history, physical examination, and laboratory evaluation. Proportions with 95% confidence intervals (CIs) calculated using the exact binomial method will be reported. Persons who are lost to follow-up will be considered in each analysis as not having reached the outcome, according to intent-to-treat principles.

Hepatitis C treatment success. We will compare the frequency of two hepatitis C treatment endpoints in the two arms in an intent-to-treat fashion, in order to evaluate the hypotheses that PWID in the intervention arm will be more likely than those in the control arm to begin treatment and achieve virologic responses to antiviral treatment for hepatitis C. The two endpoints will be defined as follows. Antiviral treatment initiation will be defined as physically receiving the first dose of antiviral medication. Sustained virologic response (SVR) will be defined as testing HCV RNA negative 12+ weeks after treatment completion.

Cost of intervention: The HCCC and the Clinician will log time spent providing services, excluding research activities. Costs will be assigned to staff time based on prevailing national wage rates. Patient time costs will also be estimated based on time spent with staff members and will be valued based on the minimum wage because most patients are likely to be unemployed. We will describe patient-reported health care visits, employment, and incarceration that will be used as inputs to future cost or cost-effectiveness studies.

Reinfection: We will report reinfection rates in all patients in both arms who achieve SVR using time-to-event methods. If 150 participants initiate antiviral therapy (50% overall) and 120 (80%) of those achieve SVR, with 2%/month attrition (21.5%/yr), we will have 198.3 person-years of follow-up when data collection is concluded, enough for a reasonably robust estimate.

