9.4 Sample Size

Using standard methods for power calculations and $\alpha=.05$, a randomized trial comparing two arms with 150 participants in each arm will have 80% power to detect the differences in proportions of study endpoints in the two arms shown in Figure 3. This power will be sufficient to detect meaningful differences between the study arms and achieve our study aims. For example, we will have 80% power to detect a difference if 66% of participants initiate antiviral therapy in an intervention arm and 50% in the control arm do. Differences between the arms of 20% or more in any outcome will be detectable (see Figure 3). These are clinically meaningful differences and are conservative estimates of our anticipated effect sizes. *Text>*

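### Aim 1d compares side effects by arm only in people who took a dose, so the effect of Accessible Care on side effects is not identified without further assumptions

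*Combined protocol and SAP*

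**What the plan says.** Aim 1d in Section 4.2.1 describes side effects, adverse events and treatment-limiting outcomes "among all study participants who received at least one dose of antiviral medication". The next sentence adds the arm contrast: "If numbers permit, we will compare the rates in the two arms to see whether AC influences perceived side effects". The rates in question are those of the dosed participants just described. No adjustment, bound or caveat is attached.

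Section 9.2 hypothesises that "PWID in the intervention arm will be more likely than those in the control arm to begin treatment". The power example in Section 9.4 supposes a difference "if 66% of participants initiate antiviral therapy in an intervention arm and 50% in the control arm do".

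The Protocol Summary lists safety of hepatitis C treatment among the outcomes to be compared between arms, but the Aim 1 text in Section 9.2 contains no safety analysis. Section 9.3 names intent-to-treat as the general rule for comparing outcomes.

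Events outside the dosed group are also to be recorded. Section 8.3 states: "All AEs occurring while on study must be documented appropriately regardless of relationship", with recording from consent onward and an inquiry at each study visit. Section 8.1 names "HCV Treatment-related SAEs, Hospitalizations and Deaths related to Overdose, and Overall Deaths" as safety endpoints that would trigger review. Section 8.5 has the DSMB assess data on each arm at least semiannually. No section plans a reported comparison of these events between the arms as randomised.

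**The concern.** The stated purpose of the arm contrast is causal, yet its population is defined by something that happens after randomisation and that the intervention is designed to change. If AC brings in people who would not otherwise have started, the treated AC group contains participants with no counterpart in the treated Usual Care (UC) group. A difference in side-effect rates could then reflect who was treated, and the absence of a difference could hide a real effect.

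At stake is how Aim 1d may be read. The first question in Section 9.1 concerns whether AC is safe and effective enough for active injectors to be treated successfully in appreciable numbers. A reader looking for an arm comparison on the safety side would find only this contrast.

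**Working it through.** **Inputs from the documents.** 150 per arm, 80% power and alpha 0.05 (Section 9.4); initiation 66% AC v 50% UC (Section 9.4); chi-square test (Section 4.2.1), taken as two-sided. The documents give no side-effect risk for this comparison, so every event risk below is an assumption.

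**1. The plan's own figure.** The pooled proportion is (0.66 + 0.50)/2 = 0.58.
- SE under the null = √(2 × 0.58 × 0.42/150) = 0.0570
- SE under the alternative = √[(0.66 × 0.34 + 0.50 × 0.50)/150] = 0.0562
- Power = Φ[(0.16 − 1.96 × 0.0570)/0.0562] = 80.5%

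This reproduces the stated 80%.

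**2. Size of the treated groups.** 150 × 0.66 = 99 (AC) and 150 × 0.50 = 75 (UC). Assume that anyone who would start under UC would also start under AC. The share of the treated AC group present only because of AC is then (0.66 − 0.50)/0.66 = 24%.

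**3. Treated-only rates with no causal effect.** Let r0 be the risk in those who would start in either arm and r1 the risk in AC-only starters. The UC treated rate is r0. The AC treated rate is (0.50 × r0 + 0.16 × r1)/0.66. With r0 = 20%:

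| r1 | AC treated rate | UC treated rate | Spurious difference (points) |
|---|---|---|---|
| 10% | (0.100 + 0.016)/0.66 = 17.6% | 20.0% | −2.4 |
| 20% | (0.100 + 0.032)/0.66 = 20.0% | 20.0% | 0.0 |
| 30% | (0.100 + 0.048)/0.66 = 22.4% | 20.0% | +2.4 |
| 40% | (0.100 + 0.064)/0.66 = 24.8% | 20.0% | +4.8 |

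**4. A wider range.** With r0 = 30%, the same formula and the chi-square test on 99 v 75 (normal approximation) give:

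| r1 | Spurious difference (points) | Rejection at nominal 5% |
|---|---|---|
| 15% | −3.6 | 8.4% |
| 20% | −2.4 | 6.5% |
| 30% | 0.0 | 5.0% |
| 40% | +2.4 | 6.3% |
| 50% | +4.8 | 10.2% |
| 60% | +7.3 | 16.8% |

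Aim 1e assumes 150 starters overall, not 99 + 75 = 174. Splitting 150 as 58% v 42% (87 v 63) gives −4.1 to +8.3 points over the same r1 range, so the argument does not turn on which figure is used.

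**5. What an observed difference of zero would allow.** Suppose both treated groups show 30%. Those who would start in either arm make up 0.50/0.66 = 75.8% of the treated AC group. Their rate under AC lies between (0.30 − 0.242)/0.758 = 7.6% and 0.30/0.758 = 39.6%. Against 30% in UC, the effect of AC in that group lies between −22.4 and +9.6 points.

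**6. Sampling error.** At 24.8% v 20.0%, the 95% half-width is 1.96 × √(0.248 × 0.752/99 + 0.20 × 0.80/75) = 12.4 points. From a 30% base, 99 v 75 has 80% power only for about 30% v 51%.

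**The case against.** Much of the case on the other side stands. Describing drug side effects in people who took the drug is ordinary practice, since the side effects are undefined in those who did not. The arm contrast is a single sentence, conditional on numbers and confined to perceived side effects. No powered conclusion rests on it. Side-effect interviews are monthly in both arms while on therapy (Section 4.1), which limits unequal ascertainment of perceived side effects.

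A reader might infer that AC brings in harder-to-treat people and that the contrast is therefore biased towards harm. The documents do not support that step. They hypothesise more starters, and Section 2.3 lists barriers to engagement, but nothing says that AC-only starters have a higher event risk. The bias may be negative, zero or positive, and most of the differences above are small beside the sampling error.

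A reader might also infer that an intent-to-treat contrast of every recorded event would be unbiased. It would not be automatically. The trial is open label (Section 9.5). Clinical events come from one centre's electronic record or from records requested elsewhere (Section 4.1), and for UC participants the permission to access records is described for those who start treatment (Section 7.1).

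It can also be said that safety by arm is covered by the DSMB and that intent-to-treat is the general rule. Neither settles the point. DSMB review is monitoring, not a reported estimate, and Section 8.1 says that other on-treatment side effects are not reported to it. The general rule does not displace the dosed-only population that Aim 1d sets.

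**Conclusion.** The point holds in a limited form. The treated-only arm contrast cannot be read as an effect of AC on side effects without further assumptions, and the plan states none. Under the plan's 66% v 50% and the assumption that AC deters nobody who would start under UC, 24% of the treated AC group has no UC counterpart. With no causal effect, the assumed risks give spurious differences from −2.4 to +4.8 points at a 20% base, and from −3.6 to +7.3 points at a 30% base. The bias vanishes if AC-only starters carry the same risk as the others. The documents neither assume nor test this.

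This does not mean that the treated-only table is wrong, that a bias towards harm has been shown, or that the trial's safety assessment fails. SVR and its analysis are unaffected. The change is worth making because it is cheap and because an all-randomised safety comparison is absent from both Aim 1d and Section 9.2.

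**What to change.** In Aim 1d, keep the treated-only table by arm, state that it is descriptive and non-randomised, and delete the inference about whether AC influences side effects.

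Add to Aim 1d and Section 9.2 a comparison in all 300 randomised of:
- all-cause death;
- SAEs, hospitalisations and overdose, as ascertained by the study-visit inquiry made in both arms (Section 8.3).

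Report risk or rate differences with 95% confidence intervals over one window common to both arms, fixed in advance. Section 4.1 schedules interviews to 9 months and Section 7.1 questionnaires for up to 12, so the plan must say which applies. The window should not extend into the follow-up reserved for participants with SVR, because entry to that follow-up depends on outcome. State that events found only through clinical records may be captured unequally between arms.

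The cost is a few lines of text and a few extra tables. Estimates for rare events will be imprecise, and rates in all randomised dilute drug-specific effects, which is why the treated-only table stays.
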